## **12 Study Procedures**

**12.1** There are no collaborating sites or investigators in this project.

**12.2** The study procedures are described thoroughly below:

Recruitment: Milagro patients presenting at the Southeast Heights and FCM Clinics will be approached in the waiting room or an exam room following triage and asked if they would like to voluntarily screen for a confidential study. Patients who meet eligibility criteria will be informed about the study and their option to voluntarily participate in the study. Screening will be done through REDCap and completed screening forms will be maintained with other confidential study forms.

Consent: Informed consent will be obtained from each participant before completing any research procedures. Each participant will read a document outlining the purpose and content of the research. Participants will fully understand what is expected of them throughout the research process. Participants will be made aware of potential risks, benefits, and incentives for participating in the initial meeting as well as the follow-up. During the consent process, phone numbers and other forms of contact information will be collected to perform the follow-up data collection.

Baseline Assessment: Data will be entered directly into REDCap (Research Electronic Data Capture) software via a tablet device. REDCap is a secure, web-based application designed to support data capture for research studies providing: 1) an intuitive interface for validated data entry; 2) audit trails for tracking data manipulation and export procedures; 3) automated export procedures for seamless data downloads to common statistical packages; and 4) procedures for importing data from external sources. REDCap is secure and HIPAA compliant and available for use to all UNM HSC faculty and staff.

Baseline Assessment Questions can be found in the section on study forms. Questions are self-report and may be completed individually by participants or with the support of a study staff member. Questions will include demographic variables, including age and ethnicity. Contact and locator information will be gathered.

Brief-Intervention: Twenty participants will receive a brief, MI-Guided Shame Resilience intervention. Participants will attend a one-on-one intervention with the research coordinator. The intervention will be 20-30 minutes and will be conducted in style consistent with MI. Participants will be invited to discuss their own experience with shame and how it affects them before moving into a collaborative discussion in which shame resilience strategies are introduced and practiced. The interventionist will help guide the conversation and incorporate shame resilience into the participants' own life.

All participants will receive the brief-intervention as there currently no alternative treatments or procedures for issues of shame.

Follow-up Data Collection: Telephone or in-person follow-up surveys at one month after receiving the intervention. In-person follow-ups will occur at a patients' scheduled visit to the clinic. Data collection will be surveys completed on a tablet device for privacy and security. If follow-up occurs over the phone, the interventionist will work with the participant to establish an adequate time, during the initial visit.

**12.3** We are not collecting existing or prospective data.

**12.4** Participant recruitment, consent, baseline measurements, and intervention will occur at the South East Heights clinic. Participant follow-up will occur over the phone or at the South East Heights Clinic. Data analysis will occur at the department of Family and Community Medicine.

**12.5** After completing the informed consent process participants will complete five instruments before the intervention to measure the preliminary effectiveness of the intervention. Participants will complete the instruments again during the 1-month follow-up phone call.

1. The *Measure of Subjective Well-Being* is short, five-item survey with Likert response options for subjective quality of life based on positive mood, vitality, and general interest. The tool was developed by the World Health Organization and has strong psychometric characteristics.

2. The *Shame Inventory* is a two-part survey that looks measures an individual's past month experience of shame. It provides an empirical measure for the extent and severity of overall shame experience and the severity of several possible shame events. Questions include items such as: How often do you typically experience shame? What is the intensity or severity of the shame you typically experience? To what extent does shame negatively affect your life? Response options are all on a 5-point Likert scale.

3. The *Shame Resilience Measure* is a psychometrically valid measure examining healthy shame behaviors in response to potentially shame inducing events. Participants are asked to select from response options that are more or less consistent with the Shame Resilience Theory, including communication and self-compassion, negative self-talk, and avoidance, on a 4-point Likert scale.

4. The *Willingness to Communicate about Health* is a survey made of 10 items that are rated on a 5-point Likert scale. It assesses individual's willingness to communicate to both providers and non-providers about their health. High scores indicate a greater willingness to communicate. This scale is based off the Willingness to Communicate scale (WTC), a previously standardized scale, and demonstrated a Cronbach reliability coefficient of .91.

5. The *Trauma Checklist Adult* (*Modified*) is a three part – self-report measure of symptomatic distress in adults arising from traumatic experiences. It measures aspects of post-traumatic stress as well as other symptoms found in some traumatized individuals.'s children and their families. In our analysis we are only interested in patient symptoms and are not asking them to report specific traumatic situations. Our modified checklist only includes the second and third part which asks about symptoms.

## 13 Data Analysis

**13.3** Descriptive statistics will be used to calculate rates of recruitment and retention, treatment fidelity scores, and quantitative treatment satisfaction. Detailed process notes regarding any unexpected study complications will be kept and analyzed using standardized qualitative methods. Our qualitative analytic approach for open ended satisfaction questions will follow Gläser and Laudel's framework for theory-driven qualitative content analysis to identify categories and patterns related to the main domains of the questions asked. Notes will be reviewed for systematic themes and

subthemes, and coded inductively. The extractions will be reduced, refined, summarized, and catalogued. To further explore patterns within each theme or sub-theme, data will be examined and organized for coherence, and further interpretations will be developed.

To address Aim 1: We will conduct a qualitative analysis to assess the feasibility of providing brief shame resilience training to the Milagro population. The feasibility of study methods and satisfaction with the intervention will be measured using the following measures.

1. *Recruitment Feasibility* will include the number of patients approached, the proportion who agree to be screened, eligibility rates, and consent rates.
2. *Retention Feasibility* will include rates of baseline completion, intervention completion, and follow-up rates at 1-month.
3. *Treatment Fidelity*: Fidelity to the intervention will be measured by the MITI 4.2.1. MITI is a one-pass behavioral coding system designed to measure treatment fidelity for motivational interviewing. It can be used for clinician training or as a quality check in clinical trials. The instrument has proficiency cut-points for a range of interventionist behaviors.
4. *The Treatment Satisfaction Questionnaire* will measure treatment satisfaction using five, Likert style questions focused on quality and delivery.
5. *The Treatment Satisfaction Interview* will include an open-ended, interview-guided discussion of treatment satisfaction. The interviews will be audio-recorded
6. *Treatment Attendance* will be measured by comparing changes in past month proportion of Milagro appointments attended prior to and after the intervention, based on a medical record abstraction.

To address Aim 2: Within group changes in targeted outcomes including well-being, shame, shame resilience, willingness to communicate about health, and treatment attendance. We will analyze the within-group data using one sample t-tests comparing baseline and follow-up means for each measure. In addition, we will calculate standardized effect sizes comparing baseline and follow-up scores, using Cohen's d. Exploratory analyses will compare all measures using a correlation matrix at both baseline and follow-up, particularly looking at the interaction between shame resilience and each measure.

Fidelity and Quality: The research coordinator will meet with the study PI, a clinical psychologist, weekly for clinical supervision during the intervention phase of the study. All sessions will be audio-recorded and scored by the PI using an established MI fidelity rating tool called the Motivational Interviewing Treatment Integrity Scale 4.2.1.

**13.4** The main purpose of this Pilot is to assess feasibility for a future clinical trial. Data from this pilot will be used in a future power analysis.

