### **Aim 1: Assess the feasibility of study methods (recruitment and retention), intervention fidelity, and treatment satisfaction.**

We will track rates of participation in the study as well as retention at follow-up. All intervention sessions will be audio-recorded and rated using the Motivational Interviewing Treatment Integrity tool. Participants will provide quantitative ratings of treatment satisfaction. In addition, a random sample of ten participants will be invited to complete qualitative interviews on treatment satisfaction.

Hypotheses: The study sample will be recruited during the study timeline and a  $\geq 85\%$  follow-up rate will be attained. Coded intervention samples will meet benchmarks for proficiency on a validated treatment fidelity rating tool. Participants will report high satisfaction with the intervention.

**Aim 2: Examine the preliminary effectiveness of the intervention on well-being, shame, shame resilience, and treatment attendance.** We administer a battery of validated questionnaires at baseline and 1-month follow-up. We will analyze within-group changes in effectiveness outcome variables. Standardized measures of effect size will be calculated.

Hypotheses: The intervention will lead to significant improvements in well-being, shame, shame resilience, and treatment attendance.

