**16.9** Assessment and medical record abstraction data will be coded with a unique identifier. A key linking participants to their unique identifier will be kept in a password protected file that is only accessible to study staff.

**16.10** Intervention performance evaluations are measured by the MITI instrument. A percentage of all interventions will be evaluated for quality, and regular feedback will be given to the study interventionists. Weekly meetings will take place between the study interventionists and the evaluator to facilitate communication and quality improvement

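### Aim 1 judges intervention fidelity by a motivational interviewing measure alone, so a session that left out the shame resilience content could still meet the fidelity criterion

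*Combined protocol and SAP*

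**What the plan says.** Section 12.2 (Brief-Intervention) describes a one-to-one session of 20-30 minutes for twenty participants, conducted in an MI style. The participant first discusses her own experience of shame, and the session then moves to a "collaborative discussion in which shame resilience strategies are introduced and practiced". Section 2.1 sets out the four behaviours of Shame Resilience Theory: seeking to understand shame, practising critical awareness, reaching out, and speaking shame. It adds that the theory has not yet been turned into a replicable intervention.

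For fidelity, 13.3 item 3 states: "Fidelity to the intervention will be measured by the MITI 4.2.1". It then says "MITI is a one-pass behavioral coding system designed to measure treatment fidelity for motivational interviewing" and "The instrument has proficiency cut-points for a range of interventionist behaviors". The Aim 1 hypothesis in section 1 is: "Coded intervention samples will meet benchmarks for proficiency on a validated treatment fidelity rating tool".

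On coverage, Aim 1 says "All intervention sessions will be audio-recorded and rated using the Motivational Interviewing Treatment Integrity tool", and the Fidelity and Quality paragraph of 13.3 says "All sessions will be audio-recorded and scored by the PI". Section 16.10 instead says "A percentage of all interventions will be evaluated for quality", giving neither a percentage nor a selection rule.

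**The concern.** The intervention has two parts: a manner of talking (MI) and a subject matter (shame resilience strategies). The subject matter is the new element, and the fidelity criterion looks only at the manner. A skilled MI conversation that never reached the strategies would breach 12.2, yet the stated criterion would not detect it.

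This matters because the pilot is meant to help formulate the intervention (2.4), to refine it (3.3) and to supply effect sizes for a larger trial (3.3, 13.4). If the Aim 1 report says that fidelity was achieved, readers will take this to cover the whole intervention. Whoever then interprets a null or a positive Aim 2 change, or plans the next trial, would have no prespecified summary of what was delivered.

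**Working it through.** The plan states no numeric fidelity figure, so there is none to reproduce. The check is whether any stated measure captures delivery of the content.

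**Step 1. Which fidelity instruments are named?** Four places name one: Aim 1 in section 1, item 3 of 13.3, the Fidelity and Quality paragraph of 13.3, and 16.10. All four name the MITI and no other tool. Both descriptions in 13.3 present it as a measure of MI fidelity.

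**Step 2. Does any other measure score content delivery?**

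- Weekly supervision by the PI (13.3) could catch an omission informally, but it yields no score and no rule that enters Aim 1.
- The satisfaction questionnaire and interview (13.3 items 4 and 5) record participants' opinions.
- Intervention completion (13.3 item 2) is counted under retention, with no definition of what content makes a session complete.
- The Shame Resilience Measure (12.5) is a participant outcome at baseline and one month, not a record of what the interventionist did.
- The monthly safety review (section 14) looks for unanticipated events.
- The audio recordings (16.13) exist to measure interventionist fidelity, but the only scoring specified for them is the MITI.

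**Step 3. Set the requirement beside the criterion.** Section 12.2 requires MI style and shame resilience strategies. The Aim 1 hypothesis requires proficiency benchmarks on one rating tool, identified as the MITI. The second requirement in 12.2 has no counterpart in the hypothesis.

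**Step 4. Count.** One fidelity instrument is named. Four behaviours are listed in 2.1, and none has a stated delivery score. Up to 20 sessions are affected.

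**Step 5. What could 20 sessions show if content were scored?** If all 20 sessions delivered a given component, the exact two-sided 95% interval has lower limit (0.025)^(1/20) = exp(-3.689/20) = exp(-0.1844) = 0.832. So 20 of 20 would support a delivery rate of at least about 83%. That is informative for a pilot and uses recordings the plan already makes.

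**Step 6. Coverage.** Aim 1 and 13.3 have every session rated, and 16.10 has an unspecified share evaluated. The wording conflicts. This is separate from the content gap and adds nothing to it.

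**The case against.** The strongest reply is that 12.2 already obliges the interventionist to introduce and practise the strategies, that every session is recorded, and that the PI both scores the sessions and supervises weekly. On this view non-delivery is unlikely and could be found by listening again. Much of this stands. The content is unscored, not unrecorded, and a generic MI session would be a departure from the plan. The reply does not remove the gap: the Aim 1 criterion as written would pass such a session, and a check made after the results are known is weaker than a prespecified score.

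A reader might also infer more than the documents support:

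- *That this gap is what prevents Aim 2 changes from being attributed to shame resilience.* It is not. Section 3.3 chooses a within-group design, so even perfect content scores in 20 of 20 sessions would leave time, standard care and MI contact as explanations.
- *That a null result could never be separated from non-delivery.* The recordings would allow a later check. What is missing is a planned one.
- *That each session must deliver all four behaviours and none is being checked against that rule.* Section 2.1 lists the four as theory, while 12.2 speaks only of strategies. No passage requires all four in one session.
- *That fidelity will rest on a small coded subset.* Section 16.10 gives no percentage, and both Aim 1 and 13.3 say all sessions.

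Two limits of evidence also stand. The protocol gives neither the MITI items nor the cut-point values, so the view that the tool does not score this content rests on the protocol's own description of it. The study forms were not available for this review, so a session guide or checklist cannot be ruled out. If one exists, 13.3 does not cite it.

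**Conclusion.** The point holds as a gap in the fidelity criterion. Aim 1 sets out to judge fidelity to the intervention, but the stated measure covers only its MI component. A session lacking the shame resilience content could meet the criterion, and this applies to any of the 20 planned sessions. The conclusion says what the criterion would miss. It does not predict that content will be omitted.

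It assumes that the MITI measures what 13.3 says it measures and that no content checklist sits in the unseen forms. The consequence is one of interpretation: the Aim 1 fidelity statement would be broader than its evidence, and Aim 2 results would be read without a planned record of delivery. The change should be made, although it does not threaten the feasibility purpose that 13.4 gives as the main one. The conflict over how many sessions are scored is a separate, minor correction.

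**What to change.** In 13.3 item 3, add a short content checklist that the existing rater completes on each recording already scored with the MITI. For each of the four behaviours in 2.1, mark two things: whether it was introduced and whether it was practised. Report the share of sessions delivering each component, with an exact 95% confidence interval.

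Reword the Aim 1 fidelity hypothesis so that the conclusion requires both MITI proficiency and content delivery. Before coding starts, the investigators should fix which components a session must cover and what share of sessions must meet that rule. Both choices are theirs, since the protocol does not define them.

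The cost is one form to draft and some added rating time on at most 20 recordings of 20-30 minutes, with no new participant contact. A weakness remains: the rater is the PI, who is unblinded and also supervises the interventionist. The report should say so.

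Separately, reconcile 16.10 with Aim 1 and the Fidelity and Quality paragraph of 13.3, so that one statement governs how many sessions are scored.

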**2.2** The PI has dedicated her career to the development and evaluation of brief applications of MI, including a clinical trial focused on risky alcohol use in a recently completed K23 award (K23 AA020865;) and another soon to be completed multi-site clinical trial focused on unintended pregnancy prevention from an R01 level grant (TP2AH000028;). The current proposal bridges the PI's background in addictions and pregnancy and targets a new health behavior in shame resilience. Pilot data demonstrating feasibility and initial efficacy will be needed in order to secure a larger grant. Co-Investigator [name] is the Medical Director of the Milagro Clinic. He will shortly be conducting a sabbatical at X in which he will be focusing on treatments for shame and trauma with this clinical population. He has previously worked on treating infants who were exposed to substances during pregnancy as well as researching treatment programs of pregnant women with past trauma and substance abuse. Project Coordinator, [name], also has extensive experience relevant to shame resilience and motivational interviewing, making him ideal to carry out the study intervention and evaluation aspects of the proposal. [name] recently graduated with honors from UNM's psychology department, where his senior thesis, which is currently under review for publication found a significant association between shame resilience and well-being, providing support for the theoretical mechanisms underlying shame resilience theory. [name] has worked extensively with the PI for the past year and is skill MI interventionist.

**2.3.** [name] recently graduated with honors from UNM's psychology department, where his senior thesis, which is currently under review for publication found a significant association between shame resilience and well-being, providing support for the theoretical mechanisms underlying shame resilience theory.

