**2.4.** Based on the existing literature this research is the next reasonable step in establishing the efficacy of the shame resilience theory. To our knowledge this is the first shame resilience intervention to be established and examined. This project will add to the current literature by expanding our knowledge of shame and by providing quantitative evidence to the leading theory of managing shame. Continuing research with a pilot study is important to evaluate and formulate the intervention as well as how the intervention is administered. Participant feedback will be important in finalizing the intervention for a future clinical trial. A smaller group will allow for both quantitative and qualitative data. Allowing us to incorporate measurable changes and participant suggestions.

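### The exploratory correlation matrices cannot estimate the interaction they are meant to examine, and no planned analysis relates change in shame resilience to change in the outcomes

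*Combined protocol and SAP*

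**What the plan says.** Under Aim 2, Section 13.3 contains one analysis that links measures to each other: "Exploratory analyses will compare all measures using a correlation matrix at both baseline and follow-up", with the stated focus "particularly looking at the interaction between shame resilience and each measure". It names no moderator, product term, regression or mediation model, and none appears elsewhere in the protocol.

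Change over time is handled one measure at a time. Section 13.3 states "We will analyze the within-group data using one sample t-tests comparing baseline and follow-up means for each measure", and adds "we will calculate standardized effect sizes comparing baseline and follow-up scores, using Cohen's d". Aim 2 in Section 1 is consistent with this: "We will analyze within-group changes in effectiveness outcome variables". Nowhere is change in shame resilience set against change in another outcome. Section 7.3 declares no exploratory endpoints, so it does not fill the gap.

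The background gives shame resilience a larger role. Section 2.4 says the project will add to the literature by "providing quantitative evidence to the leading theory of managing shame". Sections 2.2 and 2.3 describe an earlier thesis that "found a significant association between shame resilience and well-being, providing support for the theoretical mechanisms underlying shame resilience theory".

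**The concern.** There are two separate difficulties.

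- **The target and the method do not match.** In statistical usage, an interaction means that the relation between two variables depends on a third. A table of pairwise correlations holds no information on that. An analyst who takes the sentence literally has no defined analysis to run.
- **The two time points are not used to relate resilience to outcomes.** A correlation at one visit compares women with each other. A woman with generally higher resilience may also have generally higher well-being at both visits, whether or not either one moved. The background is about what happens when shame is managed better, and a within-woman comparison is closer to that idea. The study measures each woman twice, but uses this only to test each measure separately.

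At stake is how useful an exploratory result will be. The matrices would largely repeat, in about 20 women, the kind of cross-sectional association that the background already reports. The primary feasibility results are not affected.

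**Working it through.** The plan gives no target correlation, alpha or power for this analysis, so there is no figure to reproduce. The checks below use these inputs:

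- Sample size 20 (Section 5.2).
- Follow-up of at least 85% (hypotheses under Aim 1, Section 1), so 0.85 × 20 = 17 women with paired data if the target is just met.
- Single group, no control (Section 3.3).
- All correlations below are assumed.

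**1. Can a correlation matrix show an interaction?** Take independent standard normal x and w, and two outcomes with total variance 1:

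- without a product term: y = 0.5x + 0.3w + error, error variance 1 - 0.34 = 0.66;
- with a product term: y = 0.5x + 0.3w + 0.5xw + error, error variance 1 - 0.34 - 0.25 = 0.41.

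The product xw is uncorrelated with x and with w, so it leaves no trace in the pairwise correlations. In 1,000,000 simulated records, the correlations of y with x and w were 0.499 and 0.301 without the product term, and 0.501 and 0.301 with it. The estimated product coefficient was -0.001 in the first case and 0.498 in the second. The matrices are the same, although one data set has a sizeable interaction and the other has none.

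**2. Do the two per-visit matrices determine the correlation of changes?** Let X be shame resilience and Y another outcome, with equal SDs at both visits. Write r_b and r_f for the within-visit correlations of X with Y at baseline and follow-up, r_xx and r_yy for the test-retest correlations, and c1 and c2 for the cross-time correlations (X at one visit with Y at the other). Then

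change-change r = (r_b + r_f - c1 - c2) / (2 × √((1 - r_xx)(1 - r_yy))).

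Set r_b = r_f = 0.5, r_xx = r_yy = 0.6 and c1 = c2 = c. The expression becomes (1 - 2c) / 0.8:

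| Assumed c | Change-change r |
|---|---|
| 0.2 | 0.75 |
| 0.3 | 0.50 |
| 0.4 | 0.25 |
| 0.5 | 0.00 |
| 0.6 | -0.25 |

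Each row is a valid correlation structure (the smallest eigenvalue lies between 0.1 and 0.4). The baseline and follow-up matrices are identical in every row, so they cannot distinguish changes that move closely together from changes that are unrelated or opposed.

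**3. How precise would the change analysis be?** The 95% interval is tanh(atanh(r) ± 1.96/√(n - 3)).

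- r = 0.4, n = 17: atanh(0.4) = 0.424 and 1.96/√14 = 0.524, giving -0.10 to 0.74.
- r = 0.5, n = 17: 0.03 to 0.79.
- r = 0.5, n = 20: 0.07 to 0.77.

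Approximate power at two-sided 5% for a true r of 0.5 is 54% with 17 pairs and 62% with 20. For a true r of 0.3 it is 21% and 25%. These data support estimates with intervals but not a decision based on significance.

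**The case against.** The strongest reply is that this is a matter of wording plus an optional extra. The sentence names no third variable, and Sections 2.2 and 2.3 use the word association for the same kind of relation. Interaction is therefore probably loose language, and a correlation matrix is a reasonable tool for association. Aim 2 hypothesises improvement in each outcome and does not promise a mechanism analysis. Section 13.4 gives feasibility as the main purpose. All of this stands, and it is why the point is minor.

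The proposed addition is also weak evidence. It rests on few pairs and has no control group. Most of the measures are self-reports taken at the same two visits, so a shared shift in mood or response style could make changes correlate. That stands too, and the caution belongs in the plan.

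It could also be said that one joint matrix is intended, covering both visits and including the cross-time correlations. Together with the SDs, such a matrix would imply the change-change correlations. But "using a correlation matrix at both baseline and follow-up" does not say this, and one matrix per visit is the natural reading.

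Three stronger readings are tempting, and the documents do not support them:

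- *That the change correlation is the only analysis here that bears on the theory.* The planned tests and effect sizes for shame resilience and for each outcome also bear on it: if resilience does not rise, or outcomes do not improve, that is informative.
- *That the matrices amount to many unplanned tests with a countable number of false positives.* They are specified in advance and labelled exploratory, and Section 13.3 states no significance test or alpha for them.
- *That cross-sectional correlations from this study will be presented as proof of mechanism.* The protocol reads an earlier thesis in that way, but says nothing of the kind about this analysis.

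A model in which only stable traits are correlated gives a change correlation of zero by construction. It shows what could happen and does not show what these data will contain.

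**Conclusion.** The point holds as a small, inexpensive improvement to the exploratory analysis. That pairwise correlations cannot estimate an interaction does not depend on any assumption about these data. That per-visit matrices leave the relation between changes undetermined is also general. Only the illustrated range of 0.75 to -0.25 depends on the assumed 0.5, 0.6, equal SDs and cross-time correlations of 0.2 to 0.6. It is an example, not a bound and not a forecast for this sample.

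The conclusion does not extend to the Aim 1 feasibility results or to the planned tests of change in each measure. The added analysis would describe whether women whose resilience rose more also improved more. It would not show that the intervention caused either change.

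**What to change.** Replace the exploratory sentence in Section 13.3 with text along these lines:

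> Correlation matrices at baseline and follow-up will be reported descriptively to show the association of shame resilience with each other measure. Among women with both assessments, 1-month change in shame resilience will be correlated with 1-month change in well-being, shame, willingness to communicate and treatment attendance. These correlations are exploratory estimates, reported with 95% confidence intervals and without significance claims. Because there is no control group and about 17 to 20 pairs are expected, intervals will be wide and correlated change will not be attributed to the intervention.

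If an interaction in the statistical sense is really intended, the plan should instead name the moderator and the model with its product term.

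The cost is a few lines of text and four extra correlations from data already collected. It needs no added visit, instrument or participant burden. The drawback is the limited precision shown above, which the new text states openly.
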